Once enrolled into the study, each participant will be initially randomized into one of the two intervention groups: (1) SMS + multi-media page, or (2) Phone call with a peer. For household members, randomization will occur at the family unit and all participants will receive the same intervention. All participants will be asked at the start of the study a vaccine-uptake survey regarding the following: their overall willingness to get vaccinated and willingness to vaccinate their children (if applicable); factors that increase and decrease willingness to vaccinate, and their barriers that inhibited their ability to vaccinate.

Within one week of enrollment, the participant/family unit will receive the first intervention. A study team member will follow-up with the participant(s) to determine any changes in vaccination status at the two-weeks receiving their first intervention. If the participant(s) have no changes in their vaccination status, the participant/family unit will undergo a second round of randomization within one week of this follow-up. The same two interventions will be used, so an

individual will receive *either* a second exposure to the same intervention or the intervention that they did not initially receive. After two weeks of the participant's 2nd randomization, a study team member will follow-up a second time to determine vaccination status. During each follow-up session, a study team will provide the same vaccine-uptake survey to the participant and offer to provide vaccine resources on where to obtain a vaccine for the participants. If a participant receives a vaccine an additional phone call will be performed 4 weeks after their first vaccine dose to assess if they completed the primary vaccination series. Compensation of \$100 will be provided for those individuals consenting to this study. This compensation will be provided in allotments of \$50 after completing the consent document and then \$25 after each randomization. If a participant does not need to be randomized a second time, the second \$25 will be provided when learning of the participant receiving their vaccine.

Assessing Vaccine Strategies

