The primary outcome of this study will be the percentage of individuals who received an initial vaccination within two weeks of a study intervention. Vaccine uptake will be primarily assessed by verbal confirmation of recent vaccination during a follow-up visit with a study team member. We will ask for visual documentation of the vaccine card or receipt that demonstrates the vaccine has been administered. Any participants lost to follow-up will be presumed "Unable to determine." A secondary outcome will be the number of individuals that complete their primary vaccination series within 6 weeks of their first dose.

In addition, data from the vaccine-uptake survey will analyzed for trends in willingness to vaccinate within participants. Changes promoting vaccine willingness could be indicative of an impactful vaccine intervention.

E Statistical Plan

Statistical considerations

Primary analysis

Our primary hypothesis is that the initial strategy of peer counseling will result in the highest vaccine uptake. To test this hypothesis we will use a generalized linear mixed model approach, assuming a binomial distribution and a logit link function. The intervention (peer counseling vs SMS + multimedia website) will be modeled as a fixed effect, and household will be included as a random effect to adjust for within household clustering. As this hypothesis focuses on addressing the best initial intervention, we will include only data collected through the first assessment in this analysis (~ 2 weeks following enrollment). If we find a significant difference (P < 0.05) and the proportion of vaccinated participants is greater in the peer counseling group, then we will conclude that the peer counseling is superior to the SMS + video as an initial vaccination strategy. We will also evaluate whether there is evidence of imbalance between the intervention groups for a variety of covariates including: age, race/ethnicity, sex, zip code, school district, highest education level, vaccine hesitancy, influenza vaccine history, previous COVID-19 illness, household member vaccinated, health insurance type, and perceived COVID-19 risk. If we find some evidence of a difference between the initial intervention groups (P <

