0.10) then those variables will be included in the final multivariable model to estimate the adjusted difference between the interventions. If we find no appreciable difference between the adjusted and unadjusted differences, then we will report the unadjusted difference as our primary result.

Secondary analyses

Our secondary analyses will entail analysis of non-responders as well as subgroup analyses. For those that do not respond to the initial intervention, we hypothesize that switching the intervention will result in the greatest vaccine uptake. We will use the same analytic strategy as in the analysis of the primary outcome, with the exceptions that: (1) we will only analyze participants that did not respond to the initial intervention (i.e., non-responders); and (2) we will test the null hypothesis of no difference in the proportion of participants agreeing to a vaccine between those non-responders that switched (peer \rightarrow SMS + multimedia website, SMS + multimedia website \rightarrow peer) compared to those that did not switch (peer \rightarrow Peer, SMS + multimedia website \rightarrow SMS + multimedia website).

For both the analysis of the initial intervention, and the non-responder analysis we will conduct several subgroup analyses. The subgroup analyses will entail analysis of vaccine uptake stratified by: age (<5, 5-11, 12-17, 18 and older), race (white vs black vs other), school district, health insurance, and gender identity. We will use the same analytical approach as previously discussed for the primary and secondary analyses. Results from these subgroup analyses will enable us to determine whether any of these groups modify the effect of vaccine uptake. Furthermore, estimates from these analyses (in addition to the primary analysis) are critical for understanding the factors that potentially modify vaccine uptake and applying results from our studies to other target populations with similar characteristics^{9,10}.

Sample size estimates

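### Series completion is defined over 6 weeks from the first dose, but the only call that assesses it is at 4 weeks, so completions in weeks 5 and 6 would not be counted

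*Combined protocol and SAP*

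**What the plan says.** All references are to the combined protocol and SAP.

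- **Outcome (section D2, Assessing Vaccine Strategies).** "A secondary outcome will be the number of individuals that complete their primary vaccination series within 6 weeks of their first dose".
- **Assessment (section D2, Randomization).** For a participant who is vaccinated, "an additional phone call will be performed 4 weeks after their first vaccine dose to assess if they completed the primary vaccination series".
- **Other contacts (section D2, Randomization).** The first follow-up is "to determine any changes in vaccination status at the two-weeks receiving their first intervention". If status is unchanged, "the participant/family unit will undergo a second round of randomization within one week of this follow-up". Two weeks after that randomization, "a study team member will follow-up a second time to determine vaccination status". These contacts are timed from the intervention or the second randomization, not from the first dose, and their stated purpose is vaccination status, not completion of the series.
- **Data source and coding (section D2, Assessing Vaccine Strategies).** Uptake rests mainly on what the participant reports at follow-up, with a card or receipt requested. The only coding rule begins "Any participants lost to follow-up will be presumed" and assigns such participants to an undetermined category.
- **Analysis (section E, Secondary analyses).** "Our secondary analyses will entail analysis of non-responders as well as subgroup analyses". No test is attached to series completion.

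**The concern.** The outcome definition and the assessment schedule do not agree. Because both count from the first dose, no choice of start date reconciles them. A participant who completes the series on day 35 meets the definition, but has not completed when called on day 28 and has no later contact at which completion is to be recorded.

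The plan also does not say how to classify someone who is reached at week 4 without a completing dose. That person is not lost to follow-up, and the 6-week status is simply unknown. If such participants are counted as non-completers, the result is 4-week completion reported as 6-week completion. If they are set aside as undetermined, the outcome is incomplete for exactly the people the last two weeks of the window were meant to cover.

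What is at stake is the validity of one named secondary outcome. The comparison of initial strategies and its power do not depend on it.

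**Working it through.** **1. Coverage of the window**

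- Window: 6 weeks = 42 days from the first dose (Assessing Vaccine Strategies).
- Assessing call: 4 weeks = 28 days from the first dose (Randomization).
- Days after the call: 42 − 28 = 14, and 14/42 = 33%. This is a share of days, not of completions.

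**2. Whether another scheduled contact closes the gap**

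- Vaccinated after the first follow-up: the second follow-up comes at most 7 + 14 = 21 days after the dose, before the completion call.
- Most favourable case: one household member is vaccinated straight after the first intervention and the family unit is still re-randomized because of another member. The second follow-up then comes at most 14 + 7 + 14 = 35 days after the dose on the nominal schedule, and 42 − 35 = 7 days remain uncovered. It still asks about vaccination status only.
- No registry or record look-up is described for this outcome.

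**3. Scale of the possible undercount**

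The plan gives no figure for completion, so the base has to come from its sample-size table (section E, Sample size estimates). That table reproduces. With 3.6% uptake under SMS, two-sided 5% significance and 80% power, the unpooled formula for each arm is n = [p1(1 − p1) + p2(1 − p2)] × (1.960 + 0.842)² / (p2 − p1)². This gives 356 per arm (712 in total) for +5 points and 91 per arm (182 in total) for +12 points. The design effect is 1 + (1.5 − 1) × 0.50 = 1.25, so 712 × 1.25 = 890 and 182 × 1.25 = 227.5, rounded up to 228.

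Expected first doses after the first intervention, with equal arms and before inflation for drop-out:

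- +12 points, 228 participants: 114 × 0.036 + 114 × 0.156 = 4.1 + 17.8 = 21.9
- +5 points, 890 participants: 445 × 0.036 + 445 × 0.086 = 16.0 + 38.3 = 54.3

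Two quantities are assumed because the documents do not give them: that everyone with a first dose completes by week 6 (the upper limit for this base), and the share of those completions that fall after day 28.

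| Share completing on days 29–42 (assumed) | Missed of 21.9 | Missed of 54.3 |
|---|---|---|
| 0% | 0 | 0 |
| 10% | 2.2 | 5.4 |
| 30% | 6.6 | 16.3 |
| 50% | 10.9 | 27.1 |

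In relative terms the undercount equals the assumed share itself: of every 100 completions by week 6, the plan would record 100, 90, 70 or 50.

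**The case against.** The dates are not in dispute, so the case on the other side is about weight.

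- **The loss is not certain.** The plan schedules a call at 4 weeks but does not forbid a later one, and participants have a hotline, an email address and a phone number. This is true, but none of these is tied to recording completion. The loss describes the plan as written; late calls or unplanned contacts would reduce it.
- **The counts are illustrative.** This stands. The late shares are assumed and include zero. The planning rates are themselves loose: section E describes 3.6% as an increase over a no-reminder group in the text and as an uptake rate under the table, and the 15% is for agreeing to a vaccine. Section D2 also admits people who are not up to date, whereas section C (Study Setting and Populations) requires no previous dose, so some may not be starting a primary series.
- **The base covers only doses after the first intervention.** This also stands. If the same rates held among non-responders, randomized equally (an assumption), the second stage would add about 206 × 0.096 = 20 or 836 × 0.061 = 51 first doses. The figures of 22 and 54 therefore do not bound the whole outcome, although the proportional undercount is unchanged.
- **The household case and the missing coding rule are secondary.** The first depends on whether a unit with one vaccinated member is re-randomized, which the text does not settle. The second follows from the same timing mismatch. Neither is needed for the conclusion.
- **No test depends on this outcome.** Correct, and it limits the severity. It does not make the label on the reported count accurate.

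**Conclusion.** The concern holds. A 6-week outcome assessed once at 4 weeks leaves 14 of its 42 days unobserved, and no other scheduled contact reaches day 42. Any error in the count is downward, and it is zero only if nobody completes on days 29 to 42.

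Confidence in the mismatch is high, because it rests on two explicit statements with the same starting point. The number of completions lost cannot be known from the documents; the counts above show scale only and rest on the stated assumptions. With only a few dozen first doses expected at each stage, a handful of missed completions would show in the result. This should be fixed, but it is a measurement fault in one secondary outcome and does not touch the trial's main conclusion.

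**What to change.** Reconcile Randomization and Assessing Vaccine Strategies in section D2 in one of two ways.

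1. **Keep the 6-week outcome.** Make the completion call at or shortly after 6 weeks from the first dose, and record the date of the completing dose from the card or receipt, so that a late call can still be classified against day 42. This needs no additional contact, but vaccinated participants are followed for two more weeks. The plan already requests a card or receipt when asking about uptake; using it at the completion call may be a small added procedure.
2. **Keep the 4-week call.** Restate the outcome as completion by 4 weeks. This changes one line, but the outcome is narrower and no longer measures 6-week completion.

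Under either option, state that a participant reached at the call with no completing dose inside the window is a non-completer, and reserve the undetermined category for those who are not reached. Neither option changes the primary analysis or the sample size.

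### Willingness to vaccinate is to be analysed as a trend within participants, which cannot separate an intervention effect from time and loses responders by the second follow-up; compare the randomised arms instead

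*Combined protocol and SAP*

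**What the plan says.** Section D2, Randomization, sets the survey schedule. At entry, "All participants will be asked at the start of the study a vaccine-uptake survey", covering among other things overall willingness to be vaccinated. Later, "During each follow-up session, a study team will provide the same vaccine-uptake survey to the participant and offer to provide vaccine resources".

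The same section decides who reaches the second follow-up: "If the participant(s) have no changes in their vaccination status, the participant/family unit will undergo a second round of randomization", and "After two weeks of the participant's 2nd randomization, a study team member will follow-up a second time to determine vaccination status". People who are vaccinated instead get a call four weeks after their first dose about completing the series. No willingness survey is mentioned for that call.

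Section D2, Assessing Vaccine Strategies, gives the whole willingness analysis in two sentences after the primary and secondary outcomes: "data from the vaccine-uptake survey will analyzed for trends in willingness to vaccinate within participants", followed by "Changes promoting vaccine willingness could be indicative of an impactful vaccine intervention". Section E (Statistical Plan) models vaccine uptake only. It gives no arm comparison, time point, model or missing-data rule for willingness.

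**The concern.** The plan suggests that favourable movement in willingness may show that an intervention works, but the analysis it names makes no stated use of the randomisation. Two things stand in the way of that reading.

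- **Time is uncontrolled.** Everyone receives a peer call or an SMS with a link. A shift from baseline may reflect outside events, regression to the mean in a group enrolled for incomplete vaccination, or the vaccine resources offered at each follow-up in both arms. A trend cannot apportion these.
- **The last survey is selected on the outcome.** People whose willingness led to vaccination after the first stage are not in the second follow-up. The arm that vaccinates more loses more of its willing members.

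At stake is a secondary message of the trial. General drift could be credited to the interventions, and the willingness of those left at the second follow-up could be mistaken for that of everyone enrolled.

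**Working it through.** **1. Who answers each survey (section D2, Randomization).**

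| Survey | Who is covered | Randomised comparison it supports |
|---|---|---|
| Start of study | All participants | Baseline for both initial arms |
| First follow-up, two weeks after the first intervention | All participants still in contact | Initial arms, before any selection on response |
| Second follow-up, two weeks after the second randomisation | Only those with unchanged vaccination status | Second-stage groups among non-responders |

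**2. Numbers per arm.** The plan gives no figure for willingness, so I take sizes from the uptake table in section E, Sample size estimates. That table is reproduced exactly by

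n per arm = ceil[(1.960 + 0.842)² × (p1(1 − p1) + p2(1 − p2)) / d²],

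with p1 = 0.036, p2 = p1 + d, 80% power, and two-sided alpha 0.05 and 1:1 allocation assumed.

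- d = 0.05: 7.849 × (0.0347 + 0.0786)/0.0025 = 355.7, so 356 per arm, total 712.
- d = 0.12: 7.849 × (0.0347 + 0.1317)/0.0144 = 90.7, so 91 per arm, total 182.

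Multiplying by the design effect 1 + (1.5 − 1) × 0.50 = 1.25 and dividing by 0.80 for dropout gives the stated 1113 and 285. The checks below use 91 and 356 per arm as effective sizes.

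**3. Drift with no intervention effect (assumed values).** Suppose willingness moves by s SD in both arms alike, with pre-post correlation r = 0.5. The standard error of mean change in one arm is sqrt(2(1 − r)/n), which is 0.105 SD at n = 91 and 0.053 SD at n = 356. The chance that a within-arm pre-post test is significant at 5% is:

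| Common drift | 91 per arm | 356 per arm |
|---|---|---|
| 0.1 SD | 16% | 47% |
| 0.2 SD | 48% | 97% |

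The drift cancels in a between-arm comparison, which stays at 5%.

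**4. Selection into the second follow-up (assumed correlations).** Let willingness be standard normal with correlation ρ to the tendency to be vaccinated, and let a fraction v be vaccinated after stage 1. Mean willingness among those left shifts by −ρ × φ(c)/(1 − v), where c is the 1 − v quantile of the normal distribution. The values of v follow from the section E table: 3.6% for SMS, and 3.6% + 5% = 8.6% up to 3.6% + 12% = 15.6% for peer.

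| | ρ = 0.3 | ρ = 0.5 | ρ = 0.7 |
|---|---|---|---|
| SMS, 3.6% | −0.025 | −0.041 | −0.057 |
| Peer, 8.6% | −0.052 | −0.086 | −0.120 |
| Peer, 15.6% | −0.085 | −0.142 | −0.198 |
| Gap (peer minus SMS), 8.6% | −0.027 | −0.045 | −0.063 |
| Gap (peer minus SMS), 15.6% | −0.060 | −0.101 | −0.141 |

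The artificial gap is thus about 0.03 to 0.14 SD against the arm that vaccinates more. It is a gap in levels among those left. A strictly paired analysis would show it only if change in willingness, not just its level, is related to vaccination.

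**5. What the randomised comparison could detect.** At 80% power the detectable difference is 2.80 × sqrt(2/n): 0.42 SD at 91 per arm and 0.21 SD at 356. With baseline adjustment at an assumed correlation of 0.5, multiply by sqrt(1 − 0.25) = 0.866, giving about 0.36 and 0.18 SD.

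**The case against.** The strongest reply is that this is one hedged, exploratory remark. It says change could be indicative, sets no test or threshold, and is absent from section E. The document also uses the word within loosely for among (section B has examples), so "trends in willingness to vaccinate within participants" may not mean a strict before-after analysis. Both points stand and limit the importance. They do not remove the problem: on either reading no arm comparison is stated, and the interpretation still rests on change over time.

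A reader might infer more than the documents support:

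- **That the bias is large.** Suppose 30% are willing at baseline, nobody changes their mind, and every vaccination (15% peer, 3.6% SMS) comes from the willing. Those left would be (0.30 − 0.15)/0.85 = 17.6% willing against (0.30 − 0.036)/0.964 = 27.4%. This is an extreme cross-sectional arm comparison. Within-person change is zero in it by assumption, so it does not measure error in the trend the plan describes. No document gives the 30%.
- **That the survey is the plan's test of its motivation hypothesis.** Section C (Framework/theory) offers motivation as a rationale, but nothing designates the survey as its test.
- **That participants join while ill or exposed.** Section C also allows tests for travel, events or work. Section D2 requires separate consent with time to decide, and section E foresees recruitment beyond testing.

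A further fair objection concerns the remedy: counting the vaccinated as willing builds the uptake outcome into the willingness outcome. That stands, so this coding belongs only in a sensitivity analysis.

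**Conclusion.** The point holds at moderate importance. A trend in willingness within participants, with two active arms, cannot support the suggested reading of impact, and the second follow-up survey leaves out first-stage responders by design. A randomised comparison is available from the same data at the first follow-up, before that selection occurs.

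The size of any distortion cannot be derived from the documents. The 0.03 to 0.14 SD gap rests on assumed correlations of 0.3 to 0.7, a normal model and the plan's uptake rates. The drift probabilities rest on an assumed common shift of 0.1 to 0.2 SD and a pre-post correlation of 0.5. The text should not be read as committing the sponsor to claim efficacy from change alone. The uptake analyses and the sample size are unaffected.

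**What to change.** In section D2, Assessing Vaccine Strategies, with a matching line in section E:

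1. Make the willingness analysis a comparison of the randomised initial arms at the first follow-up, in all participants surveyed, adjusted for baseline willingness and with the household random effect already planned.
2. Analyse reported willingness as answered. Add a sensitivity analysis that counts people vaccinated by then as willing, and say that this coding partly restates uptake.
3. At the second follow-up, compare only between second-stage randomised groups among non-responders, adjusted for willingness at the first follow-up.
4. Report within-participant trends as descriptive, and reword the closing sentence so that only a between-arm difference is read as an effect.

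The cost is wording and one extra model, with no new data collection. The comparison estimates peer call versus SMS only. Without an untreated arm it cannot show whether either intervention raises willingness in absolute terms, and the report should say so.

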We powered this study to test the primary hypothesis that an initial intervention of peer counseling will result in greater vaccine uptake compared to the SMS + multimedia website intervention. The sample size needed to test this hypothesis was based on pilot data as well as scientific literature on vaccination uptake. One research study estimated an increase COVID-19 vaccine uptake rate of 3.6% with a text reminder treatment compared to a holdout arm that did not receive a reminder^{11C}. Our listening session data from our community members, felt that receiving vaccination information from a peer would be helpful in becoming vaccinated. Additionally, peer counseling has been noted to increase breastfeeding rates in different race/ethnicity groups of at least 15%. For this reason, we estimate that 15% of participants will agree to a vaccine after having a conversation with a peer. Pilot data available for the study population indicated that the median household size was 1, and for the power analysis we assume 1 person per household but in the main analyses we will include a random effect to account for possible clustering at the household level if there is greater than one person per household. The aforementioned estimates from the literature served as our targets, but due to the inherent uncertainty in the application of results from prior studies to different target populations, we estimated the necessary sample sizes for a range of vaccine uptake-rates (Table 1). Based on these estimates we anticipate that a total drop-out adjusted sample size (peer counseling, SMS + multimedia website) ranging from 285 (increase in vaccine uptake of 12%) to 1113 (increase in vaccine update of 5%) would provide a minimum of 80% power to detect the

effect of interest. These sample sizes are attainable as we already have approximately 1000 unvaccinated individuals that we can contact for enrolment. Additionally, we will be adding more school districts to be eligible for testing. Lastly, we will recruit for enrollment beyond just testing as we utilize our community partners to help us with recruitment.

Increase in % uptake of vaccine	Total sample (unadjusted for drop out)	Total sample size + design effect*	Total sample (adjusted for 20% drop out)			
5%	712	890	1113			
7%	416	520	650			
9%	282	353	442			
12%	182	228	285			

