Table 1. Sample size estimates for different scenarios comparing the peer intervention to the SMS + multimedia website intervention. All scenarios assume 80% power and a 3.6% vaccine uptake rate for SMS + multimedia website based on results from Dai et al. 2021. *Design effect assumes an intracluster correlation of 0.50 and an average cluster size of 1.5.

Data management

All testing data are maintained in a secure, password-protected REDCap database. Information collected on paper forms is stored in locked filing cabinets on a restricted-access floor at WUSM. Prior to undergoing testing, participants will complete a HIPAA authorization form and/or informed consent to allow SARS-CoV-2 testing data to be shared with the State of Missouri. All participants are assigned an ID number, and testing information is kept separate from the demographic data. Subjects who test positive are contacted by phone to be given their results. This information will be shared only with the participant unless an informed consent is signed that will allow sharing of their data with the RADx-UP Coordination and Data Collection Center.. Data are stored using HIPAA-compliant encryption to comply with all local, state, and national regulations for health-related data.

Our existing Consortium Data Reporting Unit (CDRU), in collaboration with our data manager, will coordinate the submission of common data element metrics on SARS-CoV-2 testing-related outcomes to the RADx-UP CDCC at Duke University. We will comply with data sharing as mandated by the NIH and follow guidance provided by the CDCC for data acquisition, collection, and curation, including appropriate consent for data sharing and implementation of the schemas proposed under the ABOUT ML effort. The CDRU will also ensure compliance with federal, state, and local requirements and policies for testing, reporting, and surveillance. The CDRU will also work closely with the CDCC to employ a common set of tools to promote collection of comparable data on social determinants of health, including measures from the PhenX Toolkit. Effective implementation strategies for rapid adoption will be disseminated through the CDCC.

We will work collaboratively with the Duke CDCC in reviewing and revising our data collection tools to ensure we are collecting the appropriate CDEs. We will share our data with Duke

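### Baseline vaccine willingness is surveyed in everyone, but its nearest listed covariate enters the primary model only on chance imbalance, so the analysis is valid but less efficient than it could be

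*Combined protocol and SAP*

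**What the plan says.** Section E, Primary analysis, specifies a logistic mixed model with household as a random effect. On the fixed side, "The intervention (peer counseling vs SMS + multimedia website) will be modeled as a fixed effect". Peer counselling is declared superior under this rule: "If we find a significant difference (P < 0.05) and the proportion of vaccinated participants is greater in the peer counseling group".

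The same paragraph lists 12 baseline covariates, vaccine hesitancy among them, to be tested for imbalance between the arms. Where a covariate differs at P < 0.10, "then those variables will be included in the final multivariable model to estimate the adjusted difference between the interventions". The unadjusted result is still the primary one unless adjustment changes it appreciably, a term the plan does not define.

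Section D2, Randomization, has all participants surveyed at the start of the study on topics that include "their overall willingness to get vaccinated and willingness to vaccinate their children (if applicable"). The survey is repeated at each follow-up. Parents answer for children under 18 (D2, Recruitment and Consent). The only analysis stated for these answers is of trends in willingness (D2, Assessing Vaccine Strategies).

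The sample-size table makes no allowance for covariate adjustment: "All scenarios assume 80% power and a 3.6% vaccine uptake rate for SMS + multimedia website".

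**The concern.** A baseline covariate improves a randomised comparison because it predicts the outcome. Whether the arms happen to differ on it is a separate matter. A balance test therefore applies the wrong criterion: it will usually leave out a strongly prognostic variable and may let in one that predicts nothing.

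Willingness is a natural candidate here. Section C, Framework/theory, says the interventions are meant to raise motivation and so change behaviour, and the outcome is vaccination within two weeks. With uptake of a few percent in the SMS arm there will be few events, so any avoidable noise matters. What is at stake is power and precision at the same enrolment. The validity of the comparison is not in question.

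**Working it through.** **1. The plan's own sample sizes.** Inputs from Sample size estimates: SMS uptake p1 = 0.036, increase d = 0.05 to 0.12, power 80%. Two-sided 0.05 and 1:1 allocation are not stated, but they reproduce the table.

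N = 2 × ceil[(1.960 + 0.842)² × (p1(1−p1) + p2(1−p2)) / d²]

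- 5% row: 7.849 × (0.034704 + 0.078604) / 0.0025 = 355.7, so 356 per arm and N = 712.
- 12% row: 7.849 × (0.034704 + 0.131664) / 0.0144 = 90.7, so 91 per arm and N = 182.
- The 7% and 9% rows give 416 and 282.

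The table note says: "Design effect assumes an intracluster correlation of 0.50 and an average cluster size of 1.5". That gives 1 + (1.5 − 1) × 0.50 = 1.25. Multiplying by 1.25 and dividing by 0.80 gives 1113, 650, 442 and 285. Every cell matches, with no covariate term anywhere.

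**2. How often the screen admits hesitancy.** Under sound randomisation and a valid test, P < 0.10 occurs about 10% of the time. If the 12 covariates were independent, at least one would enter with probability 1 − 0.9^12 = 0.72, prognostic or not.

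**3. Expected events at the unadjusted N.** N/2 × (p1 + p2):

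- 5% row: 356 × 0.122 = 43.4
- 7% row: 208 × 0.142 = 29.5
- 9% row: 141 × 0.162 = 22.8
- 12% row: 91 × 0.192 = 17.5

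**4. Power gain by simulation.** The documents give no prognostic strength, so it is assumed: a four-level item (40/30/20/10%), a constant odds ratio per level, marginal uptake held at the plan's values, no clustering, likelihood-ratio test, 2000 replicates.

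| Odds ratio per level | Gain in power (points) | Fall in variance of standardised risk difference |
|---|---|---|
| 1 | no loss | none |
| 1.5 | about 0-1 | about 0-2% |
| 2 | about 1-2 | about 1-6% |
| 3 | about 3-4 | about 7-9% |
| 4 | about 5-6 | about 11-16% |

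The simulation standard error of one power figure near 83% is √(0.83 × 0.17 / 2000) = 0.8 points. Repeat runs of the same set-up agreed to within a point or two.

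**5. Second method.** Asymptotic variance was computed with a standard normal covariate x. Let m_t(x) be the uptake probability at x, with m_0 for the SMS arm and m_1 for the peer arm.

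- Unadjusted: V = 2[p1(1−p1) + p2(1−p2)]
- Adjusted: V = E[2m_1(1−m_1) + 2m_0(1−m_0)] + Var(m_1 − m_0)

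The design effect was held at 1.25. At assumed odds ratios per SD of 1.65, 2.7 and 4.5:

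- 5% row: variance ratios 0.985, 0.936 and 0.858, so 1113 becomes about 1096, 1042 and 955.
- 12% row: ratios 0.979, 0.920 and 0.840, so 285 becomes about 279, 262 and 239.

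**6. The logit scale.** In the 5% row (N = 712) the log odds ratio rises from 0.924 to 0.938, 0.987 and 1.080. Its standard error also rises, from 0.342 to 0.344, 0.353 and 0.370. Wald power goes from 77.2% to 77.8%, 79.9% and 83.1%. The gain is in power; the standard error of the log odds ratio does not shrink.

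**The case against.** The strongest reply is that nothing promised is lost. The unadjusted comparison is legitimate and the sample size is built on it. That stands, and it makes this a matter of efficiency only.

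Four stronger readings are tempting, and the documents do not support them.

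- **A reader might infer that the primary analysis can only ever contain intervention and household.** It can contain more: hesitancy has a conditional route in. The documents also do not say whether hesitancy is measured by the willingness survey.
- **A reader might infer that a willingness score exists and is ready to use.** D2 lists survey topics and gives no scale or scoring.
- **A reader might infer that the gain is large and certain.** Prognostic strength is not given. Odds ratios of 3 and 4 per level mean 27-fold and 64-fold odds between the lowest and highest of four levels. At 1.5 to 2 the gain is 0-2 points.
- **A reader might infer that adjustment is free and narrows the interval in the planned model.** It does not narrow the log odds ratio interval (step 6), and it needs design decisions.

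Two technical cautions also stand. The simulation had no clustering, so the gain under the planned household random effect is untested. The likelihood-ratio test is also somewhat liberal with so few events. Null rejection was about 6% for both tests in one run, and in another about 8-9% unadjusted and 7-8% adjusted at N = 182. Unadjusted Wald power at N = 182 is about 73-77%, against roughly 82% by likelihood ratio. The differences in step 4 are therefore more informative than the power levels behind them.

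**Conclusion.** The point holds as one of efficiency. By admitting covariates on a balance test, the plan will, in about 9 trials in 10, leave out the listed variable closest to the willingness it collects from everyone.

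Under the assumptions of step 4, pre-specified adjustment is worth between 0-1 and 5-6 power points, and between 0-2% and 11-16% of the variance of the standardised risk difference. The asymptotic check gives a similar range, with required N falling by about 2% to 16%. Where the trial would fall in these ranges depends on a prognostic strength that the documents do not state. The change is worth making because it uses data already collected and showed no loss when willingness predicts nothing.

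**What to change.** In section E, Primary analysis:

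1. Pre-specify baseline willingness as one ordinal covariate in the primary model, whatever the baseline balance. For participants under 18, use the parent's willingness to vaccinate the child. This replaces entry by the P < 0.10 screen.
2. Name a standardised risk difference as the primary estimate. It matches an outcome defined as a percentage and is the scale on which the precision gain appears. State how it is averaged over the household random effect.
3. State that the survey is completed before allocation is revealed. D2 mentions the survey after the randomisation step, so the order is unclear.
4. Do the same for the non-responder comparison, using willingness at the first follow-up. D2 already collects it, and the second randomisation comes afterwards.

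**Cost.** No new data and no extra enrolment. The plan must define a scale for the item, covering both adults' own answers and parents' answers, and a missing-value rule such as a missing category. With only about 17 to 43 events expected at the unadjusted sample sizes, the covariate set must stay small.
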